Attachment 2. Adverse Events of Special Interest List of Preferred Terms

Adverse Event of Special Interest	Source	Preferred Term
ALT/AST elevation	(Modified) Liver related investigations, signs and symptoms (SMQ) narrow, (MedDRA v23.1)	Alanine aminotransferase abnormal Alanine aminotransferase increased Aspartate aminotransferase abnormal Aspartate aminotransferase increased Hepatic enzyme abnormal Hepatic enzyme increased Hepatic function abnormal Hypertransaminasaemia Liver function test abnormal Liver function test increased Transaminases abnormal Transaminases increased
Renal Complications	(Modified) Acute renal failure (SMQ) broad (MedDRA v23.1)	Acute kidney injury Anuria Nephropathy toxic Oliguria Renal failure Renal impairment Subacute kidney injury Blood creatinine abnormal Blood creatinine increased Creatinine renal clearance abnormal Creatinine renal clearance decreased Creatinine urine abnormal Creatinine urine decreased Crystal nephropathy Glomerular filtration rate abnormal Glomerular filtration rate decreased Nephritis Proteinuria Renal function test abnormal Renal tubular disorder Renal tubular dysfunction Renal tubular injury

Adverse Event of Special Interest	Source	Preferred Term
Cholesterol increase	Dyslipidaemia (SMQ), (MedDRA v23.1)	Renal tubular necrosis Urine output decreased Nephropathy Nephropathy toxic Glomerulonephropathy Nephrolithiasis Blood cholesterol abnormal Blood cholesterol esterase increased Blood cholesterol increased Dyslipidaemia High density lipoprotein abnormal High density lipoprotein decreased High density lipoprotein increased Hypercholesterolaemia Hyperlipidaemia Hypo HDL cholesterolaemia Intermediate density lipoprotein decreased Intermediate density lipoprotein increased LDL/HDL ratio decreased LDL/HDL ratio increased Lipid metabolism disorder Lipids abnormal Lipids increased Lipoprotein abnormal Lipoprotein increased Low density lipoprotein abnormal Low density lipoprotein decreased Low density lipoprotein increased Non-high-density lipoprotein cholesterol decreased Non-high-density lipoprotein cholesterol increased Primary hypercholesterolaemia Remnant hyperlipidaemia Remnant-like lipoprotein particles increased Total cholesterol/HDL ratio abnormal Total cholesterol/HDL ratio decreased Total cholesterol/HDL ratio increased Very low density lipoprotein abnormal

Adverse Event of Special Interest	Source	Preferred Term
		Very low density lipoprotein decreased
		Very low density lipoprotein increased
Hematologic abnormalities	(Modified) Haematopoietic cytopenias affecting more than one type of blood cell (SMQ), (MedDRA v23.1)	Aplastic anaemia Autoimmune aplastic anaemia Bicytopenia Bone marrow failure Cytopenia Febrile bone marrow aplasia Full blood count decreased Gelatinous transformation of the bone marrow Immune-mediated pancytopenia Pancytopenia Panmyelopathy Aspiration bone marrow abnormal Biopsy bone marrow abnormal Blood count abnormal Blood disorder Bone marrow disorder Bone marrow infiltration Bone marrow myelogram abnormal Bone marrow necrosis Bone marrow toxicity Haematotoxicity Myelodysplastic syndrome Myelodysplastic syndrome transformation Myelofibrosis Myeloid metaplasia Plasmablast count decreased Scan bone marrow abnormal
Hematologic abnormalities	(Modified) Haematopoietic erythropenia (SMQ), (MedDRA v23.1)	Aplasia pure red cell Aplastic anaemia Erythroblast count decreased Erythroid maturation arrest Erythropenia Hypoplastic anaemia

Adverse Event of Special Interest	Source	Preferred Term
		Microcytic anaemia Proerythroblast count decreased Red blood cell count decreased Reticulocyte count decreased Reticulocytopenia Anaemia Erythroblast count abnormal Erythropoiesis abnormal Haematocrit abnormal Haematocrit decreased Haemoglobin abnormal Haemoglobin decreased Leukoerythroblastic anaemia Normochromic anaemia Normochromic normocytic anaemia Normocytic anaemia Proerythroblast count abnormal Red blood cell count abnormal Reticulocyte count abnormal Reticulocyte percentage decreased
Hematologic abnormalities	(Modified) Haematopoietic leukopenia (SMQ), (MedDRA v23.1)	Agranulocytosis Band neutrophil count decreased Band neutrophil percentage decreased Basophil count decreased Basophilopenia B-lymphocyte count decreased Cyclic neutropenia Eosinopenia Eosinophil count decreased Febrile neutropenia Granulocyte count decreased Granulocytes maturation arrest Granulocytopenia Idiopathic neutropenia Leukopenia Lymphocyte count decreased Lymphopenia

Adverse Event of Special Interest	Source	Preferred Term
		Metamyelocyte count decreased
		Monoblast count decreased
		Monocyte count decreased
		Monocytopenia
		Myeloblast count decreased
		Myelocyte count decreased
		Neutropenia
		Neutropenic infection
		Neutropenic sepsis
		Neutrophil count decreased
		Promyelocyte count decreased
		Pure white cell aplasia
		T-lymphocyte count decreased
		White blood cell count decreased
		Basophil count abnormal
		Basophil percentage decreased
		B-lymphocyte abnormalities
		B-lymphocyte count abnormal
		Differential white blood cell count abnormal
		Eosinophil count abnormal
		Eosinophil percentage decreased
		Full blood count abnormal
		Granulocytes abnormal
		Leukopenia neonatal
		Lymphocyte count abnormal
		Lymphocyte percentage abnormal
		Lymphocyte percentage decreased
		Monocyte count abnormal
		Monocyte percentage decreased
		Mononuclear cell count decreased
		Myeloblast percentage decreased
		Myelocyte percentage decreased
		Myeloid maturation arrest
		Neutrophil count abnormal
		Neutrophil percentage decreased
		Plasma cell disorder
		Plasma cells absent
		White blood cell analysis abnormal

Adverse Event of Special Interest	Source	Preferred Term
		White blood cell count abnormal
		White blood cell disorder
Hematologic abnormalities	(Modified) Haematopoietic thrombocytopenia (SMQ), (MedDRA v23.1)	Acquired amegakaryocytic thrombocytopenia Megakaryocytes decreased Platelet count decreased Platelet maturation arrest Platelet production decreased Platelet toxicity Thrombocytopenia Megakaryocytes abnormal Platelet count abnormal Platelet disorder Plateletcrit abnormal Plateletcrit decreased

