2.3.2.2. Potential Risks

All therapies have the potential to cause adverse experiences. In addition, the discontinuation of NA treatment bares a risk of hepatitis B flares.

Patients with positive HBV DNA and positive HBsAg can always experience increases in liver transaminases which may indicate immune activation and may result in the reduction of viral parameters such as HBV DNA and/or HBsAg. Whether this occurs at higher frequency during or after treatment with JNJ-6379 and JNJ-3989 is not known.

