 - At regular time points throughout the study (see [Schedule of Activities](#)), blood samples for biochemistry, blood coagulation, and hematology and urine samples for urinalysis, urine chemistry, and renal biomarkers will be collected. Vital signs (systolic and diastolic blood pressure, pulse rate, and body temperature), height (only at screening), body weight, and electrocardiograms (ECGs) will be recorded throughout the study. Physical examinations will be performed and AEs will be assessed (see Section 8.2, Safety Assessments). Events of Special Interest will be closely monitored (Section 8.3.6, Adverse Events of Special Interest).

An Independent Data Monitoring Committee (IDMC) will be established for continuous monitoring of SAEs, AEs leading to discontinuation, and ALT flares to ensure the continuing safety of the participants enrolled in the current study (see Section 9.6, Independent Data Monitoring Committee). In addition, an Independent Flare Expert Panel (IFLEP) will be appointed to characterize and adjudicate each ALT flare (see Section 9.7, Independent Flare Expert Panel).

After stopping treatment with NA and JNJ-3989 and JNJ-6379, participants will be monitored closely during the follow-up phase, with frequent follow-up visits and pre-defined NA re-treatment criteria in case of flares (Section 6.7, NA Re-treatment Criteria and Monitoring After Stopping of NA).

The post-treatment monitoring and NA re-treatment criteria were further updated based on findings from a case of post-treatment HBV reactivation with subacute hepatic failure and assessment of additional REEF-2 study data (see Section 6.7).

JNJ-3989 will be administered using a proper subcutaneous technique to decrease the risk of ISRs. ISRs will be managed as outlined in Section 8.3.6, Adverse Events of Special Interest.

Any clinically significant abnormalities persisting at the end of the study/early discontinuation will be followed up by the investigator until resolution (return to baseline) or until stabilization (to be agreed upon with the sponsor).

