8.3.6.3. Intervention-emergent ALT/AST Elevations

Elevated liver enzyme activity can be triggered by the underlying HBV disease as well as by the study intervention.

Management of intervention-emergent ALT/AST elevations is presented graphically in Section 10.6, Appendix 6, Intervention-emergent ALT/AST Elevations and is described below.

Any intervention-emergent elevation of ALT and/or AST $\geq 3x$ ULN and $\geq 3x$ nadir (ie, lowest value during study participation) should trigger an assessment of confounding factors (alcohol intake, change in concomitant medication, and comorbidities) and should trigger a confirmatory study visit to repeat laboratory testing of AFP, ALT, AST, ALP, bilirubin (total and direct), INR, albumin, and HBV DNA. Additional tests should be considered based on clinical judgement (Refer to 10.6, Appendix 6, Intervention-emergent ALT/AST Elevations). The confirmatory visit should be scheduled as soon as possible, preferably within 7 days of the receipt of the initial ALT/AST results. In case the repeat laboratory testing shows an isolated ALT/AST elevation (ie, with stable albumin, bilirubin [total and direct], and INR) the participant may continue study intervention. In case of confirmed ALT elevation $>1,000$ U/L and $\geq 3x$ baseline value, JNJ-3989 and JNJ-6379 (or their matching placebos) should be discontinued. In both cases, NA treatment should be continued. The participant will be monitored (laboratory testing of ALT, AST, ALP, bilirubin [total and direct], INR, albumin, and HBV DNA) on a weekly basis until ALT and/or AST levels have returned to $<5x$ ULN and HBV DNA is $<20,000$ IU/mL.

If the ALT and/or AST level is $\geq 3x$ ULN and $\geq 3x$ nadir and is associated with any of the following laboratory results or clinical symptoms:

- INR ≥ 1.5 , OR
- direct bilirubin $>1.5x$ ULN, OR
- serum albumin <3.0 g/dL, OR
- ascites, hepatic encephalopathy, or liver-related symptoms (eg, severe fatigue, nausea, vomiting, right upper quadrant pain in the absence of an alternative medical explanation), OR
- other indication of reduced liver function

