3.2. Independent Flares Monitoring

Flares in this study will be adjudicated by the independent Flares Expert Panel (iFLEP). The iFLEP flare adjudication results are sent to the IDMC Chairperson, and the information will include conclusions and review history for each flare. Additional details are provided in the iFLEP Charter document. Flares are defined in Section [5.3.1.1.6](#).

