5.3.2.1.3. Flares

The incidence rate will be calculated and summarized for each type of on-treatment or off-treatment flares (virologic, biochemical and clinical) separately, as well as the overall incidence of participants experiencing at least one flare, regardless of type, by study intervention arm. Additionally, for each participant the total number of flares the participant experienced will be counted by type. Such counts will be used to summarize the distribution of the total number of flares by type and by intervention arm.

For on-treatment biochemical flares, the incidence of flares causing treatment discontinuation will be summarized by intervention arm. Further, for off-treatment flares, the count and percentage of participants who experienced a flare followed by NA re-treatment will be summarized by flare type and intervention arm. Similarly, the incidence of flares followed by the achievement of HBsAg seroclearance (at any time) will be summarized by flare type and intervention arm.

For off-treatment virologic, biochemical and clinical flares, the count and percentage of participants who experienced a flare will be summarized by intervention arm and selected subgroups (i.e. by NA type at study entry, by HBsAg levels at EOT, by HBcrAg levels at EOT). Biochemical flares will also be summarized in the follow-up after NA re-treatment. The cut-offs for HBsAg and HBcrAg levels at EOT are provided in Sections 5.3.1.1.5 and 5.4.1.1.2.

Flares that are associated with signs of liver decompensation will be provided in a listing.

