6.2.2. Analysis Methods

Descriptive statistics (for example, may include n, mean, SD, minimum, median, and maximum) will be calculated for each laboratory analyte for observed values and changes from baseline at each scheduled time point by intervention arm and study phase.

Shift tables will be provided summarizing the shift in laboratory values from baseline over time with respect to abnormality criteria (low, normal, high) for each laboratory parameter by study phase.

The cross-tabulations of the worst toxicity grades over time versus baseline grade and the worst abnormalities versus baseline grade per parameter and per analysis phase will be presented including also the number of participants per worst grade and the number of participants per abnormality.

A tabulation of percentage and number of the participants who have treatment-emergent worst toxicity grades and treatment-emergent worst abnormalities per parameter, time point and per analysis phase will be included. The incidence table of worst toxicity grade abnormality in laboratory parameters will be also presented stratified by the subgroup of interests identified in Section 2.4.2.

Plots of mean (+/- SE) values and changes from baseline over time for selected laboratory parameters will be presented by intervention arm.

A listing including all parameters with at least one treatment-emergent toxicity or abnormality per participant (exclusion of urinalysis) will be generated.

Spaghetti-plots for selected laboratory parameters may be presented by intervention arm over time (with Week shown on x-axis).

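### The SAP's liver AESI list leaves out the severe tier of its own event, and no table in this SAP joins an ALT/AST rise with reduced liver function or reports adjudicated flares

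*SAP*

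**What the plan says.** Protocol 2.3.2.2 lists among the potential risks that "the discontinuation of NA treatment bares a risk of hepatitis B flares". Protocol 2.3.3 says that monitoring and re-treatment criteria were updated after "findings from a case of post-treatment HBV reactivation with subacute hepatic failure".

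Protocol 8.3.6.3 sits inside the AESI section. Its base trigger is ALT and/or AST ≥3x ULN and ≥3x nadir. It then describes a more severe tier, in which that elevation "is associated with any of the following laboratory results or clinical symptoms": INR ≥1.5, direct bilirubin >1.5x ULN, albumin <3.0 g/dL, ascites, encephalopathy or liver-related symptoms, or another sign of reduced liver function. The follow-up Schedule of Activities (1.3.2) refers back to this section, so it is relevant after NA is stopped as well.

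On outputs, the SAP says:
- **6.1.3 and Attachment 2:** AESIs are summarised by arm and phase. The ALT/AST group comes from "Modified) Liver related investigations, signs and symptoms (SMQ) narrow, (MedDRA v23.1".
- **6.2.2:** the laboratory tabulation covers participants with "treatment-emergent worst toxicity grades and treatment-emergent worst abnormalities per parameter, time point and per analysis phase will be included".
- **5.3.2.1.3:** virologic, biochemical and clinical flares are counted by arm. For the severe ones, "Flares that are associated with signs of liver decompensation will be provided in a listing".
- **3.2:** "Flares in this study will be adjudicated by the independent Flares Expert Panel (iFLEP"). The results go to the IDMC chairperson.

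**The concern.** An AESI table is where a reader of the study report looks first for liver harm. If its term list holds enzyme and liver-test terms only, plus one general function term, a mild transaminase rise is counted. A reactivation with hepatic failure coded under that diagnosis is counted only if an enzyme or liver-test term was also reported for the same participant.

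The study stops NA in both arms at Week 48, so the comparison that matters for safety is how often a flare came with loss of liver function in each arm. As the SAP stands, that has to be pieced together from a listing, from separate per-parameter tables and from preferred terms spread over the general adverse event tables. The blinded panel's judgement of each flare, the most considered view of these events, has no place in the SAP's outputs.

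**Working it through.** The plan gives no figure to reproduce here. The check is a trace of outputs, followed by a short calculation of what the missing counts could show.

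**1. The term list.** Attachment 2, ALT/AST elevation: ALT (2 terms), AST (2), hepatic enzyme (2), transaminases (2) and hypertransaminasaemia (1) make 9 enzyme terms. Liver function test terms add 2, and "Hepatic function abnormal" adds 1. Total 9 + 2 + 1 = 12. Terms for reactivation, hepatitis, hepatic failure, jaundice, bilirubin, INR, albumin, ascites or encephalopathy: 0 of 12.

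**2. Comparison with the other organs.** In the same attachment the renal group includes renal failure and acute kidney injury beside creatinine terms. The hematologic groups include pancytopenia and bone marrow failure beside cell-count terms. SAP 6.2.3.2 also defines a renal composite (serum creatinine plus at least one of three tubular markers, so 2 of 4 parameters). The liver group has no failure term, and the SAP has no liver composite.

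**3. The joint laboratory event.** Bilirubin, INR, albumin, ALT and AST are all in SAP Table 4, and SAP 6.2.2 tabulates each on its own. No output in this SAP combines ALT/AST with any of the other three. The enzyme half is already derived: SAP 5.3.1.1.6 defines a biochemical flare as confirmed ALT and/or AST ≥3x ULN and ≥3x nadir.

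**4. Where such events are counted by arm.**
- NA re-treatment: SAP 5.3.1.1.8 evaluates each sub-criterion. One of them (Protocol 6.7) is signs of decreasing liver function. SAP 5.3.2.1 gives n and %, and SAP 5.1 makes the summaries by arm.
- Adverse events: SAP 6.1.2 tabulates all, serious and grade 3 or higher TEAEs by arm and phase.

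**5. Why these do not replace the joint count.** The sub-criterion is a CRF item with example tests and no thresholds. It applies only after NA is stopped and is not linked to a flare. It belongs to SAP Section 5, whose primary set is mITT. That set drops participants who, for pandemic reasons, withdrew before Week 72 or lacked the primary assessment, so it is not the safety set. The general TEAE tables use the safety set but have no grouped liver-failure row, so related events can be split over several terms.

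**6. What a by-arm count could show.** With zero events, the exact two-sided 95% upper limit is 1 − 0.025^(1/n):
- n = 80: 1 − 0.025^(1/80) = 4.5%
- n = 40: 1 − 0.025^(1/40) = 8.8%

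The documents give no true risk. Over an assumed range, the chance of at least one event, 1 − (1 − p)^n, is:

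| Assumed risk p | n = 80 | n = 40 |
|---|---|---|
| 0.5% | 33% | 18% |
| 1% | 55% | 33% |
| 2% | 80% | 55% |
| 5% | 98% | 87% |

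**The case against.** The strongest reply is that these events are not invisible. A reader might infer from the AESI list that post-NA liver failure gets no count by arm at all. The documents do not support that: step 4 shows two routes, and flares by type are counted by arm as well. This part of the reply stands, and it limits the point to a grouped, flare-linked count.

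Second, the named AESI is ALT/AST elevations, so a list of enzyme terms fits the label. That is true of the label. But the protocol's text under that label includes the tier with reduced liver function, and the SAP's renal and hematologic groups do include failure terms.

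Third, DAIDS grades 3 and 4 for direct bilirubin already refer to signs of hepatotoxicity or liver failure. That is so, but it is a grade on one parameter, not the 8.3.6.3 combination.

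Fourth, with 80 and 40 participants and descriptive safety analyses, a listing shows each case in detail and can be counted by hand. That is fair, and the listing should stay. A planned count costs little more and fixes the denominator in advance.

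Fifth, the Master Protocol, the IDMC SAP, the iFLEP charter and the Data Presentation Specification are separate documents that were not available. They may hold further outputs, so the statement is confined to this SAP.

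It is also tempting to fault the flare algorithm for accepting an AST-only rise. That does not hold: the SAP matches the protocol's ALT and/or AST, and a clinical flare also needs confirmed HBV DNA above threshold.

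**Conclusion.** The point holds in a limited form. In this SAP, 0 of 12 liver AESI terms cover reactivation, hepatitis, hepatic failure, bilirubin, INR or decompensation. No table joins ALT/AST elevation with reduced liver function, flares with decompensation are listed only, and adjudicated flares have no output. The by-arm AESI table can therefore miss the severe tier of the event that it is meant to describe.

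The gap is in reporting. It does not touch the primary analysis, and part of the information reaches by-arm tables by other routes. Calling flares after NA stop the trial's main known harm would go too far: the protocol lists them as a potential risk, although it records one case with subacute hepatic failure. The conclusion assumes that AESI membership follows Attachment 2 as written and that no unseen document supplies these tables.

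**What to change.** - **SAP 6.1.3 and Attachment 2:** add a separate liver subgroup with the reactivation, hepatitis, hepatic failure, jaundice/bilirubin, INR, ascites and encephalopathy terms. Keep the present 12 terms as their own group, so that mild enzyme rises stay distinguishable.
- **SAP 6.2.2:** add one descriptive table by arm and phase on the safety set. It counts participants with ALT and/or AST ≥3x ULN and ≥3x nadir together with each, and with any, of the associated results already listed in Protocol 8.3.6.3. State the nadir definition and the time window for counting the results as concurrent.
- **SAP 5.3.2.1.3:** keep the listing of flares with decompensation and add a count by arm. Report flares as adjudicated by the existing panel, by arm, beside the algorithmic count.

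The cost is SAP wording and a few descriptive tables with few expected events. The adverse event, laboratory and panel data are already generated by the trial. The thresholds are the protocol's own, and no treatment, re-treatment or stopping rule changes.

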8.2.4. Clinical Safety Laboratory Assessments

Refer to Section 8.2.4 of the Master Protocol PLATFORMPAHPB2001.

In addition, urine samples for urine chemistry and renal biomarkers will be collected as noted in Section [10.2](#), Appendix 2, Clinical Laboratory Tests.

For this study, the laboratory abnormality of cholesterol increase is identified as laboratory abnormality of interest.

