8.3.6.5. Hematologic Abnormalities

Mild thrombocytopenia was observed in recently conducted non-clinical toxicology studies with the combination of JNJ-3989 and JNJ-6379. In addition, in a 3-month combination study with 80 rats, 1 rat developed pancytopenia related to bone marrow depletion after 23 days of dosing. Previously, in a 9-month dog study in 24 dogs treated with JNJ-6379 alone, pancytopenia which correlated with a marked increase in plasma cell-like cells in the bone marrow was observed in 1 dog after 60 days of dosing.

No thrombocytopenia or pancytopenia has been observed in the ongoing Jade study (56136379HPB2001) investigating JNJ-6379/Placebo with or without NA treatment. All 232 participants have completed at least 24 weeks of study treatment. In the Phase 1/2a AROHBV1001 study with JNJ-3989, mild transient thrombocytopenia (Grade 1) was observed in 6 out of 84 participants receiving 3 SC injections of JNJ-3989 alone over a period of up to 12 weeks with background of NAs. The transient thrombocytopenia was not considered clinically significant. No thrombocytopenia or pancytopenia was observed in 12 patients when JNJ-3989 and JNJ-6379 were given in combination over a 12-week period.

Based on the non-clinical findings, any relevant abnormalities in hematologic parameters will be carefully monitored as described below:

- Platelet counts: <100,000 cells/mm³ or <100 G/L or reduction from baseline by at least 50%
- Hemoglobin: Decrease of at least 2 g/dL from baseline or at least Grade 2 (DAIDS)
- Reticulocytes: Reduction to <0.5% of the RBC count
- Neutrophil count: Treatment emergent reduction to at least Grade 2 (DAIDS)

In case any one of the above criteria are met, a confirmatory visit should be scheduled as soon as possible, preferably within 7 days of the receipt of the initial results. Confirmation of the results will trigger weekly or biweekly (every other week) unscheduled visits until improvement or stabilization of the respective parameter(s). Stabilization is defined as no further significant reduction over two consecutive visits.

In case of confirmed Grade 3 or Grade 4 hematologic abnormalities, discontinuation of investigational study treatment (JNJ-3989 and/or JNJ-6379/placebo) should be considered. In case of discontinuation, NA treatment should be continued.

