6.1.3. Adverse Events of Special Interest

Incidence of treatment-emergent adverse events of special interest will be summarized by intervention arm and analysis phase. The adverse events of special interest include:

- ALT/AST elevations

- Injection Site Reactions
- Renal complications
- Cholesterol increase
- Hematologic abnormalities (platelet count, hemoglobin, reticulocytes, neutrophil count)

The list of all preferred terms belonging to ALT/AST elevations, renal complications, cholesterol increase, and hematologic abnormalities is provided in [Attachment 2](#). Injection site reactions will be identified using the eCRF Injection Site Reaction form.

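### The SAP's Cholesterol increase event list includes lipid falls, and three of the six protocol hematologic triggers, plus any confirmed trigger, have no participant count in the SAP

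*SAP*

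**What the plan says.** Protocol 8.2.4 states that "the laboratory abnormality of cholesterol increase is identified as laboratory abnormality of interest", and Protocol 8.3.6 lists events related to cholesterol increase among those of special interest. No lipid fall is named as a signal.

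On identification, SAP 6.1.3 says: "The list of all preferred terms belonging to ALT/AST elevations, renal complications, cholesterol increase, and hematologic abnormalities is provided in" Attachment 2. The fifth category is handled differently: "Injection site reactions will be identified using the eCRF Injection Site Reaction form".

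In Attachment 2 the Cholesterol increase group is sourced to the dyslipidaemia query. Its terms include "Low density lipoprotein decreased", "Non-high-density lipoprotein cholesterol decreased" and "Very low density lipoprotein decreased".

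Protocol 8.3.6.5 was added by Amendment 2 after pancytopenia in one rat dosed with the combination. It sets laboratory values for platelets, hemoglobin, reticulocytes and neutrophils that call for a confirmatory visit. The hemoglobin line, for example, begins "Hemoglobin: Decrease of at least 2 g/dL from baseline or at least Grade 2 (DAIDS". SAP 6.1.3 names the same four parameters under hematologic abnormalities but identifies events by preferred term. SAP 6.2 separately tabulates treatment-emergent worst DAIDS grade per laboratory parameter and phase, including unscheduled assessments.

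**The concern.** An AESI table is read by its row labels. A row labeled Cholesterol increase that also collects reported falls in LDL or VLDL can overstate the signal, or blur a difference between arms, without the reader knowing.

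The hematologic row has the opposite weakness. The instructions with the DAIDS table in Protocol Appendix 9 say that a laboratory abnormality need not be an adverse event. A participant can therefore meet a trigger, return for confirmation, and still be absent from the AESI table because no event was reported. The laboratory outputs then have to supply the count, and they do so for only part of the trigger set.

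**Working it through.** **Cholesterol list.** I counted the terms printed in Attachment 2. I left out six renal terms (renal tubular necrosis to nephrolithiasis) that run over from the preceding group at a page break.

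- Terms in the group: 33.
- Terms ending in decreased: 7 (HDL, IDL, LDL, VLDL, non-HDL cholesterol, LDL/HDL ratio, total cholesterol/HDL ratio).
- Hypo-HDL cholesterolaemia also names a low value: 7 + 1 = 8, and 8/33 = 24%.
- Two of the eight concern low HDL, which is not an improvement: 8 − 2 = 6, and 6/33 = 18%.

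These are shares of a term list, not event rates. The documents give no frequency for such reports.

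**Hematologic triggers.** Each limb of Protocol 8.3.6.5 is set against what SAP 6.2 counts using the DAIDS grades in Protocol Appendix 9.

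| Protocol 8.3.6.5 limb | Counted per participant in SAP 6.2? |
|---|---|
| Platelets <100 G/L | Yes: same as DAIDS grade ≥2 (grade 2 is 50 to <100) |
| Platelets down ≥50% from baseline | No |
| Hemoglobin DAIDS grade ≥2 | Yes |
| Hemoglobin down ≥2 g/dL from baseline | No |
| Reticulocytes <0.5% of red cells | No: no DAIDS grade, so normal range only |
| Neutrophils DAIDS grade ≥2 | Yes |

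Three of six limbs are counted and 6 − 3 = 3 are not. No SAP output counts participants with a confirmed trigger of any kind.

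**Do the grades stand in for the two change-based limbs?** The baselines below are assumed, across a range.

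- Platelets halved: 150 to 75 G/L is grade 2, 200 to 100 is grade 1, 250 to 125 is ungraded, and 300 to 150 is ungraded. The grade table therefore catches an exact halving at grade 2 only from a baseline below 200.
- Hemoglobin down 2 g/dL: 12 to 10 is grade 1 in both sexes, and 13 to 11 and above is ungraded.
- Larger falls can also be ungraded. Platelets 300 to 145 is (300 − 145)/300 = 51.7%, and 145 is above the grade 1 range (100 to <125). In a man, hemoglobin 15.5 to 12.0 is a fall of 3.5 g/dL, and 12.0 is above the grade 1 range (10.0 to 10.9).

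**Do the other laboratory outputs fill the gap?** SAP 6.2.2 gives change from baseline by scheduled visit and low/normal/high shift tables. The first describes a distribution in absolute units and, under SAP 2.1.3, uses one value per visit window. It neither counts participants past a cut-off nor expresses a percentage fall. The shift tables use laboratory limits, which the documents do not give, rather than the trigger values.

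**The case against.** The strongest reply is that the SAP does what the protocol asks. Protocol 8.3.6 describes events of special interest as significant adverse events, and Protocol 9.4.2 plans descriptive summaries of them, so a term-based table is consistent with it. The values in 8.3.6.5 direct monitoring at sites; they do not define an analysis variable. This stands, so the missing count is a gap in reporting and not a contradiction between the documents.

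Five stronger readings are tempting, and the documents do not support them.

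- *All AESI are found only through reported terms.* Injection site reactions come from a dedicated form. Biochemical flares (SAP 5.3.1.1.6) and renal changes (SAP 6.2.3) are also derived from laboratory values, outside the AESI table.
- *The triggers are never counted.* Three of the six limbs are, through worst grade.
- *The AESI table misses the marrow signal.* Attachment 2 includes pancytopenia, bone marrow failure and decreases in platelets, hemoglobin and reticulocytes. Such events appear if reported.
- *All eight low-value lipid terms are improvements.* Only six are.
- *The dyslipidaemia query was copied unaltered.* This is inferred from the missing word Modified, which the other query-based groups carry. The query itself is not in the documents, and the point does not need it.

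It is also fair to say that safety is descriptive, that AESI are listed individually so a misfiled lipid fall could be spotted, and that SAP 6 lets the sponsor add safety analyses. A listing and a discretionary addition are not a prespecified count by arm.

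**Conclusion.** The point holds in two parts. First, 8 of the 33 Cholesterol increase terms name a low or falling value, and 6 of those are lipid falls that run against the protocol's signal. Applied as written, SAP 6.1.3 would tabulate any such report under the wrong label. How often this would happen is unknown and may be rare. The split of six and two rests on the usual clinical reading that low HDL is unfavorable and that lower values of the other measures are not.

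Second, the hematologic AESI has no laboratory component. Three of six trigger limbs, and confirmation of any trigger, have no participant count in the SAP. A count in the IDMC SAP or the Master Protocol cannot be excluded, because neither was available.

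Neither part touches the primary efficacy analysis. Both merit correction because the SAP already counts participants by laboratory criteria for other signals: confirmed ALT/AST elevations, percentage falls in eGFR and confirmed renal tubular markers. The hematologic signal that prompted Amendment 2 has no equivalent for its change-based limbs.

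**What to change.** In Attachment 2, remove the eight low-value terms and HDL increased from the Cholesterol increase list, or show them in a separate, clearly labeled row. HDL increased is included because it is not the rise a reader would take the row to mean.

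In SAP 6.1.3 or 6.2.2, add one descriptive table by intervention arm and analysis phase giving n (%) of participants who meet each laboratory trigger in Protocol 8.3.6.5. Give the initial and the confirmed count separately, draw both from all laboratory data including unscheduled visits, and place the table beside the term-based hematologic AESI.

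The cost is one attachment edit and one extra table from data already collected. The monitoring and discontinuation rules in the protocol stay as they are.
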